## 6.4 Sample Size and Power

The factorial design has enhanced statistical power and can handle cluster randomization of schools. Our statistical methods will also estimate variation in the effect across schools over time. First, linear mixed effects models with random intercepts and slopes for school, and fixed effects for the school-level intervention, time, and time-by-intervention interaction (the estimate of interest) will be applied. Likewise, the main effect for the child-level intervention and a time\*intervention interaction term will be included in the model, and variation across multiple measurements on a child within a school will be accounted for by child-level random effects. Second, marginal models using generalized estimating equations will produce robust estimates that adjust for clustering at the school level. Third, assumption-free, randomization-test-based (permutation test) methods do not rely on assumptions of parametric models. We will use conventional levels of statistical significance (p=0.05) for all pre-specified comparisons for these aims and shall report all results to confirm consistency of findings and their robustness to model specifications. Variability of the intervention effect across schools will reflect consistency of intervention effects and thus generalizability in new settings. Both mixed effects models and permutation-test methods will estimate variance components. All contrasts noted in specific Aims 1a through 1d are handled with the same modeling specifications. This approach will also be used to account for change over time across schools, and to assess sustainability of the proposed interventions.

Missing data on covariates will be handled using formal multiple imputation as needed. The proposed mixed effects models make limited assumptions of "missing at random" (MAR). To the extent that children are lost to follow-up, we shall include in our models covariates that are associated with the probability of dropout to limit confounding by dropout. We anticipate no school withdrawals, but in case of loss, we will use all data collected until time of dropout. The primary analysis will be "as randomized" (also called intention to treat). Reporting will follow the CONSORT guidelines for randomized studies and cluster randomized designs.

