5.1.2 Patient-level analysis – mixed effects models

First, linear mixed effects models with random intercepts and slopes for school, and fixed effects for the school-level intervention, time, and time-by-intervention interaction (the estimate of interest) will be applied. Likewise, the main effect for the child-level intervention and a time*intervention interaction term will be included in the model, and variation across multiple measurements on a child within a school will be accounted for by child-level random effects. This approach then becomes a three-level model with explicitly modeled random effects at the school and child levels.

Synergy of the effect of the two interventions will be estimated by the 3-way interaction between time, the school-level intervention, and the child-level intervention along with all corresponding two-way interactions.

Models will use numerical quadrature with least 12 quadrature points. Models with 16 quadrature points will be used to check sensitivity of results to numerical integration.

This and other individual-patient-level methods can be more efficient (smaller confidence bounds) than cluster (school)-level models. (Hayes and Moulton, section 11.4.2)

We shall exploit mixed effects models to estimate the degree of variation of effects across the 36 schools, both the 18 intervention schools and the 18 control schools by estimating the random slope component of variance and asking whether the observed variation across schools is greater than that expected at random.

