5.1.3 Patient-level analysis – marginal models

Second, marginal models using generalized estimating equations (Fitzmaurice 2011) will produce robust estimates that adjust for clustering at the school level. These methods tend to be robust for

non-continuous outcomes (non-identify link models) and those outcomes will likely apply to our outcomes of asthma control (possibly a log gamma model) and number of symptom days (possibly a log link Poisson or negative binomial model). In contrast to mixed effects models, marginal models do not rely on numerical integration. In addition to generalized estimating equations, quasi-least squares regression (Shults and Hilbe, 2014) will also be implemented. Quasi-least squares regression is an approach for estimation of the correlation parameters that is in the framework of generalized estimating equations; it allows for application of correlation structures that were previously unavailable for generalized estimating equations and can sometimes be implemented when generalized estimating equations fails to converge.

Marginal models tend to work poorly for designs with small numbers of clusters. In our case, the number of clusters (36) is relatively large. Nevertheless, we shall implement at least one method for adjusting for a number of clusters that is not large, as implemented in Stata's program xtgeebcv program (Gallis 2019) and R's program "saws" (Fay and Graubard 2001).

5.1.4 School-level analysis -- randomization-test-based methods.

Third, assumption-free, randomization-test-based (permutation test) methods that do not rely on assumptions of parametric models will also be applied. (Berger, 2000; Good, 2005; Small, 2008; Tang 2009; Rosenbaum 2002). (Also see Hayes and Moulton 2017)

We will use conventional levels of statistical significance (p=0.05) for all pre-specified comparisons for these aims. We shall not apply Bonferroni corrections for estimates from different modeling methods that use the same specification.

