We shall report all results to confirm consistency of findings and their robustness to model specifications. Variability of the intervention effect across schools will reflect consistency of intervention effects and thus generalizability in new settings. Both mixed effects models and permutation-test methods (Lee 2012) will estimate variance components to support generalizability. This approach will also be used to account for change over time across schools, and to assess sustainability of the proposed interventions.

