6.1.1 School level characteristics

School characteristics appear in Table 6.1a. Because the number of factors when cross classified is large (3*3*4=36) relative to the total number of schools in the sample, effect modification by school will be based on post-hoc ordering of schools by their predicted level of improvement, standardized by child characteristics. With mixed effects models that include random intercepts and slopes for school, we propose to order each school in the intervention group by its "prediction" (the combination of expected value and random effects) at both baseline and at month 12. This ordering will (a) account for measurement error in the outcome of interest (the main outcome is asthma control), (b) adjust estimates by the number of observations at the child level over time, and (c) permit consideration of both the level at baseline and the trend over time of the degree of asthma control. By contrasting for each school the change over time in predicted asthma control levels for children enrolled in the study from that school, we can identify the schools with the most improvement and the least improvement. A description of the characteristics of the high (and low) performing schools will then support conclusion (and generate hypotheses) about school-level factors related to the success (or failure) of the intervention.

Table 6.1a

School Subgroups as candidate effect modifiers	HYPOTHESIS
(1) FCI,(2) school absenteeism rate,(3) poverty level	Children going to schools with poorer FCI, higher school absenteeism rate and greater # of households living below poverty level will demonstrate the least amount of improvement with school intervention
(1) Climate,(2) leadership,(3) positive attitudes	Schools will improve more from the intervention if at baseline they have more positive climate, stronger implementation leadership, and more positive attitudes towards evidence-based practice.
 (1) Charter vs Non-charter (2) < 500 students vs > 500 students (3) Facility score Index (4) Census tract 	 H1: students who attend charter schools will achieve greater reduction of missed school days during the intervention H2: schools with lower FCI's will have more asthma triggers which will lead reduced improvement in missed school days H3: improvement in school absences from the intervention will differ based on census tract of school (effect modification by census tract)

Descriptive analysis of schools:

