The main effects of A and S take into account that any interaction will affect the main effects. If the interaction is synergistic, then the "main effects" will be larger than just the A term or the S term alone. Main effects in this context are the marginal effects (of A and S), and these marginal effects are larger if there is a synergistic interaction (if the interaction is negative, then of course, the marginal effects are smaller).

We assume a design effect for the S+ S- effect (cluster randomized, and now 36 clusters (18+ 18)). If we assume effect size variation across sites (schools) of 0.0 to 0.5, then sd of random intercept is about 0.125. That would mean that if sigmasq= 1.0, then sigmasq(b) = 0.125*0.125. =0.016. If we assume that the variation in effect size is broader (0 to 1.0), then sd= 0.25 and sigmasq(b) = 0.25*0.25 = 0.0625. We used this broader assumption. Then ICC = 0.0625/(1.0625) = 0.06 and DEFF= 1+0.06*11 (assuming cluster size = 12) = 1+0.66= 1.66.

Plan is as follows.

Using program from Oct 2016, recreate power with 36 sites and 12 patients per site (n=432 overall). Results appear in the Table below.

Contrast	Contrast	Stipulated			Power	Power
	(Table cell)	Effect size(sd)			(n=600)	(n=432)
		А	S	A,S		
S+ v S-	a,b vs c,d	0.35	0.5	0.0	0.96	0.97
A+ v A-	a,c vs b,d	0.35	0.5	0.0	0.99	0.95
S+A+ v S-A+	a vs c	0.35	0.5	0.0	0.89	0.88
S+A+ v S+A-	a vs b	0.35	0.5	0.0	0.87	0.75
S- A+ v S-A-	c vs d	0.35	0.5	0.0	0.85	0.71
S+,A- v S-A-	b vs d	0.35	0.5	0.0	0.89	0.83
		А	S	A,S		
S+ v S-	a,b vs c,d	0.35	0.5	0.25	0.99	0.99
A+ v A-	a,c vs b,d	0.35	0.5	0.25	0.99	0.99
S+A+ v S-A+	a vs c	0.35	0.5	0.25	0.99	0.99
S+A+ v S+A-	a vs b	0.35	0.5	0.25	0.99	0.99
S- A+ v S-A-	c vs d	0.35	0.5	0.25	0.85	0.71
S+,A- v S-A-	b vs d	0.35	0.5	0.25	0.89	0.83

Power for contrasts of interest. Effect sizes are in terms of Cohen's d nomenclature and represents the fraction of standard deviations of change over time.

A=Navigator effect; S=School Effect; AS= interaction; "+" = , "-" = control

Cells e, f are not included in this table for simplicity and to be conservative.

Power to detect main effects

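### The pooled school slope variance in SAP 5.1.2 measures differences in school trend, not variation in the intervention effect, and should not be read as evidence on consistency or generalizability

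*SAP*

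**What the plan says.** SAP 5.1.2 (the section on mixed effects models; the number 5.1.2 is used twice) specifies "linear mixed effects models with random intercepts and slopes for school". The school intervention, time and their interaction are fixed effects. So are the child-level intervention and its interaction with time. Child-level random effects cover repeated measurements. The section then says how variation of effects will be judged: "by estimating the random slope component of variance and asking whether the observed variation across schools is greater than that expected at random". The schools that enter this variance are those of the two arms together, "both the 18 intervention schools and the 18 control schools".

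Section 5.1.2 does not name the covariate of the slope. SAP 6.1.1 shows that it is time: predictions from the same model are taken for each school at baseline and month 12, and they "permit consideration of both the level at baseline and the trend over time of the degree of asthma control".

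SAP 5.1.4 gives the interpretation: "Variability of the intervention effect across schools will reflect consistency of intervention effects and thus generalizability in new settings". It also sets the test level: "We will use conventional levels of statistical significance (p=0.05) for all pre-specified comparisons for these aims". Protocol 6.4 makes the same promise: "Our statistical methods will also estimate variation in the effect across schools over time".

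**The concern.** A random slope on time says how much each school's trend departs from the mean trend of its arm. In a control school that departure cannot be variation in the school-intervention effect, because the school did not receive the intervention. In an intervention school it is the school's own background trend plus any departure of its effect from the average. Each school is seen under one condition only, so a single variance over both arms cannot separate the two parts. Testing it against zero asks whether schools differ in trend, which is a different question from whether the intervention works unequally.

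For the child-level intervention the position is reversed. It is randomized inside every school, so variation of its effect between schools can be estimated. That needs a school-level random coefficient on A by time, and SAP 5.1.2 gives A fixed terms only. As specified, the model estimates the variation of neither effect.

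At stake is the plan's statement on generalizability. Ordinary differences between schools could be published as an inconsistent intervention effect. If the A effect does vary, the mixed-model interval for A would also be too narrow for the new settings to which the plan wants to generalize.

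**Working it through.** **Inputs.** From SAP section 8 (power revised 04/2019): 36 schools (18 and 18) of 12 children, 432 in all; outcome is change over time in SD units; residual variance 1; school SD 0.25 (variance 0.0625), with a narrower value of 0.125 (variance 0.0156) also considered. Test level 0.05 from SAP 5.1.4.

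**The plan's own figures.**
- ICC = 0.0625/1.0625 = 0.0588, rounded to 0.06.
- Design effect = 1 + 11 × 0.06 = 1.66, as stated.
- Power of S+ versus S- at an effect of 0.5: effective n per arm = 216/1.66 = 130.1. Power = Φ(0.5 × √(130.1/2) − 1.96) = Φ(2.07) = 0.98. With total SD √1.0625 = 1.031 in place of 1, power is 0.975. The SAP states 0.97, so the inputs are read correctly.

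**Rate of reporting variation when the effect is identical everywhere.** Let v be the background variance of school trend, equal in both arms. The between-school mean square divided by the within-school mean square follows (1 + 12v) × F with 36 − 2 = 34 and 36 × 11 = 396 degrees of freedom. The 5% critical value is 1.459, so the rejection rate is P(F > 1.459/(1 + 12v)).

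| Background variance v | ICC | 1 + 12v | Reports variation |
|---|---|---|---|
| 0 | 0 | 1.00 | 5% |
| 0.0156 | 0.015 | 1.19 | 18% |
| 0.0309 | 0.03 | 1.37 | 37% |
| 0.0417 | 0.04 | 1.50 | 51% |
| 0.0625 | 0.059 | 1.75 | 74% |

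A simulation with five visits per child, child random slopes (assumed variance components) and a REML likelihood-ratio test gave 4%, 16%, 36% and 70% at ICC 0, 0.0154, 0.03 and 0.0588 (1,500 trials each).

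**The test does not separate the two sources.** In 40,000 simulated trials per setting, background variance 0.03 with no effect variation led to rejection in 36%. Effect variance 0.0625 in S+ schools with no background variance led to rejection in 38%. A significant result therefore does not show that the effect varies. In the second setting 62% of trials miss real variation, so a non-significant result does not show consistency.

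**The A effect without its random coefficient.** Suppose the A effect varies between schools with SD 0.25 (assumed).
- Variance under the model: 2/216 = 0.00926.
- True variance: 0.00926 + 0.0625/36 = 0.01100.
- True SE over model SE: √(0.01100/0.00926) = 1.09, so the model SE is too small by 1 − 1/1.09 = 8%.
- Size of the nominal 5% test: 2Φ(−1.96/1.09) = 7.2%; simulation also gave about 7%.
- With a school-clustered sandwich variance and a t reference, simulated size was 4.1%.

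**Comparing slope variances between S+ and S- schools.** The difference equals Var(effect) + 2 Cov(background trend, effect). With both SDs 0.25, so that the true effect variance is 0.0625, a correlation of −0.5 gives 0.0625 − 0.0625 = 0, and +0.5 gives 0.0625 + 0.0625 = 0.125. As a test (F on 17 and 17 df, one-sided 5%) it holds its size at 4.9% to 5.3%. Its power at effect SD 0.25, with zero covariance, is 30%, 25%, 22% and 17% for background variance 0, 0.016, 0.03 and 0.0625.

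**The case against.** **The text may be under-specified and not wrong.** Section 5.1.2 does not name the slope covariate, and its mention of the two groups of schools could mean estimation in each. It states no arm-specific variance and no comparison between arms, however, and 6.1.1 settles that the slope is a trend. The rule as written is one variance read as effect variation.

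**Effects may mean the child-level intervention, which is compared within all 36 schools.** That would make the count of 36 sensible. It does not rescue the rule, because a school slope on time is not a school-specific A effect.

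**The A interval is protected elsewhere.** This largely stands. The SAP will report all three approaches, and the GEE analysis in 5.1.3, with robust variance clustered by school and a small-sample correction, already allows for A-effect variation. The understated SE affects the mixed model only.

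**The SAP is already cautious.** Section 6.1.1 calls effect modification by school exploratory, and 9.2 expects attempts to show heterogeneity to fail. Neither caveat is attached to the generalizability statement in 5.1.4. The warning in 9.2 is about missing heterogeneity, whereas the risk here also includes reporting it where there is none.

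**Stronger readings to avoid.** A reader might infer that the test will usually report variation that is not there. The documents do not support this, because they give no background trend variance. Section 8 derives 0.0625 from an assumed range of effect sizes (0 to 1.0), although it then enters as a random intercept and design effect shared by all schools. A reader might also take SD 0.25 as the plan's assumption for A. Section 8 introduces that range for the S contrast, and no range is given for A.

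**Conclusion.** The rule is wrong as written. The pooled school slope variance mixes background trend differences with S-effect variation and says nothing specific about A. It cannot carry the conclusion on consistency and generalizability in either direction.

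The size depends on a quantity that the documents do not state. With no true effect variation, 36 equal schools of 12, and the planning figures used as background values by assumption, the false-report rate runs from about 5% through 18% to 74%. It stays at 5% only if schools share the same background trend. The A-effect consequence is modest: an SE about 8% too small and a 5% test at about 7%, in one of three reported analyses, if the effect SD were 0.25.

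The primary S-by-time estimate is not in question. A school random slope is appropriate there, since it lets the S comparison reflect differences in trend between schools. The fault lies in the reading given to the variance.

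**What to change.** In SAP 5.1.2 and 5.1.4:

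1. Describe the pooled school slope variance as variation in school trend. Remove it, and its test against zero, as evidence on effect variation or generalizability.
2. Add a school-level random coefficient for A by time. Report its variance with an interval as the variation of the A effect, and keep the term in the mixed model that gives the A interval.
3. Optionally, report slope variances separately in S+ and S- schools with an interval for the difference, labelled exploratory. State that the difference equals the S-effect variance only if effect and background trend are uncorrelated, and that power is about 17% to 30% at an effect SD of 0.25. The zero-correlation condition is not a safe default, since SAP 6.1.1 itself hypothesizes that benefit depends on facility condition, absenteeism and poverty.

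The matching sentences in Protocol 6.4 should be read in the same way. The cost is SAP wording and a few variance parameters, some of which may be estimated at zero with about 12 children per school. No new data are needed.

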5.1.3 Patient-level analysis – marginal models

Second, marginal models using generalized estimating equations (Fitzmaurice 2011) will produce robust estimates that adjust for clustering at the school level. These methods tend to be robust for

non-continuous outcomes (non-identify link models) and those outcomes will likely apply to our outcomes of asthma control (possibly a log gamma model) and number of symptom days (possibly a log link Poisson or negative binomial model). In contrast to mixed effects models, marginal models do not rely on numerical integration. In addition to generalized estimating equations, quasi-least squares regression (Shults and Hilbe, 2014) will also be implemented. Quasi-least squares regression is an approach for estimation of the correlation parameters that is in the framework of generalized estimating equations; it allows for application of correlation structures that were previously unavailable for generalized estimating equations and can sometimes be implemented when generalized estimating equations fails to converge.

Marginal models tend to work poorly for designs with small numbers of clusters. In our case, the number of clusters (36) is relatively large. Nevertheless, we shall implement at least one method for adjusting for a number of clusters that is not large, as implemented in Stata's program xtgeebcv program (Gallis 2019) and R's program "saws" (Fay and Graubard 2001).

5.1.4 School-level analysis -- randomization-test-based methods.

Third, assumption-free, randomization-test-based (permutation test) methods that do not rely on assumptions of parametric models will also be applied. (Berger, 2000; Good, 2005; Small, 2008; Tang 2009; Rosenbaum 2002). (Also see Hayes and Moulton 2017)

We will use conventional levels of statistical significance (p=0.05) for all pre-specified comparisons for these aims. We shall not apply Bonferroni corrections for estimates from different modeling methods that use the same specification.

We shall report all results to confirm consistency of findings and their robustness to model specifications. Variability of the intervention effect across schools will reflect consistency of intervention effects and thus generalizability in new settings. Both mixed effects models and permutation-test methods (Lee 2012) will estimate variance components to support generalizability. This approach will also be used to account for change over time across schools, and to assess sustainability of the proposed interventions.

5.2 Adjustments for sparse cells

In the event that one or more schools fails to fill the cells a, b, c, d with at least one child, we shall make the following adjustments in the definition of strata (clusters). Any school that contains zero cells will be joined with the "nearest" school assigned to the same intervention group, where nearest is determined by the same school randomization factors. This pooling of schools will be done without knowledge of the outcomes. At that time, and for all analyses of child outcomes, the pooled schools will be treated as one for analysis. Implications for analysis of association of implementation and outcome will require discussion.

If no children were recruited in any school, then that school will be dropped from the analysis.

If a school lacks a child in one of the two child-level randomization groups, then the school will be lumped with another school in the same treatment arm and in the same randomization stratum, or the closest stratum, and if there is more than one such school, then with the school that has the smallest number of recruited children.

